8.1.5.5. Group 2B: Days 32 to 37 (At home)

On Days 32 to 37, the participant is to self-administer doxycycline 100 mg po every 12 hours at home at about the same times (\pm 30 min) each day. The participant will continue with the e-diary as described in [Section 8.3.5.1](#). The site must contact the participant to remind them to start their third course of doxycycline within 24 hours of Day 31.

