IP Group	Treatment Group	Treatment	Sample Size (N)	
1 Cipro	1A	AV7909 + ciprofloxacin (with PK assessment)	≈40	≈70
	1B	AV7909 + ciprofloxacin (without PK assessment)	30	
2 Doxy	2A	AV7909 + doxycycline (with PK assessment)	≈40	≈70
	2B	AV7909 + doxycycline (without PK assessment)	30	
3 AV7909	3	AV7909 only	70	
		TOTAL	≈210	

Approximately the first 40 participants who are randomized for either IP Groups 1 and 2, ie, the first 80 participants randomized across all sites to either antibiotic group, will be assigned to Treatment Groups 1A or 2A while those randomized into IP Groups 1 and 2 thereafter will be assigned to Treatment Groups 1B or 2B. Randomization will be stratified by site. A representative racial distribution will be sought among recruited participants and sites will be asked to recruit populations that are gender- and age-balanced (ie, between 40-60% male with 40-60% of participants in the two age ranges of 18 to 30 years of age and 31 to 45 years of age).

[Figure 1](#) displays the overall design used for this study.

Ciprofloxacin (500 mg by mouth [per os] every 12 hours [po q 12 hr]) will be administered to Group 1 on Days 4-9, Days 22-24 and Days 31-37, and doxycycline (100 mg by mouth [per os] every 12 hours [po q 12 hr]) will be administered to Group 2 on Days 2-9, Days 22-24, and Days 32-38. Antibiotics will be administered in three courses that will be used both by site staff for in-clinic visits and by participants when they are at home. The exact format of the courses in terms of number of tablets and when participants will receive each course will be described in the Pharmacy Manual.

The 40 participants in Group 1A will self-administer approximately half (14/31) of the ciprofloxacin doses; the remainder will be administered by site staff during clinic visits. The 30 participants in Group 1B, with far fewer clinic visits than Group 1A due to the lack of PK sampling, will self-administer more than 90% (29/31) of ciprofloxacin doses.

AV7909 Anthrax Vaccine

IND 014451

Protocol EBS.AVA.210, Version 3.0 (28 October 2019)

For the doxycycline groups, the distributions of self-administered doses are similar to those planned for the two ciprofloxacin groups with Group 2A self-administering 15/35 doses and Group 2B self-administering 33/35 doses.

An event schematic for this study is provided in [Figure 2](#).

Ciprofloxacin PK sessions in Group 1A will be conducted on Days 4, 8, 31 and 35.

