Independent safety oversight will be provided by a Data Safety Monitoring Board (DSMB), which will be notified of significant AEs (refer to [Section 8.5](#)) as determined by the medical monitor (MM) on an ongoing basis. The DSMB will comprise at least three voting members, to include one expert in immunology to specifically support the evaluation of potential AESIs for autoimmune etiology, if pre-existing or new onset, and relationship to the study product. The DSMB will make recommendations regarding the safety of continuing enrollment and dosing. Study enrollment and dosing may be interrupted at the request of the DSMB Chair if it is believed that an AE represents a significant safety concern requiring suspension of dosing pending full DSMB evaluation. The operations of the DSMB will be detailed in a DSMB Charter.

AV7909 Anthrax Vaccine
 IND 014451
 Protocol EBS.AVA.210, Version 3.0 (28 Oct 2019)

Figure 1: Study Design for EBS.AVA.210

cipro = ciprofloxacin; doxy = doxycycline; PK = pharmacokinetics; po = per os, (oral); q12 h = every 12 hours; TNA = toxin-neutralizing antibody; TSH = thyroid-stimulating hormone

^aIn Group 1, the evening dose on Day 37 is not administered ^bAntibiotic dosing for Groups 1 & 2 up to Day 8 is to enable 2 PK sessions prior to vaccination #1 (vac #1) on Day 8. Dosing continues on Day 9, extends around vac #2 (on Days 22 to 24) and then discontinues until Day 31 (cipro) or Day 32 (doxy). Cipro dosing continues from Day 31 to Day 37 and doxy dosing continues from Day 32 to Day 38, encompassing 2 PK sessions after the complete vaccination regimen as well as the blood draw for TNA. ^cSolid lines at Days 1, 8, 23, 37 and 51 are days when all groups have in-clinic visits. Days in red are those when Groups 1A and/or 2A have clinic visits for blood draws for pre-dose, trough values or PK.

[figure not shown]

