4.1.4. Group 2B Schedule

As shown in [Figure 2](#) except for clinic visits for PK and trough value sampling, the 30 participants in Group 2B will receive otherwise identical treatment to those in Group 2A. They will have blood drawn at randomization (Day 1) for TNA, TSH and autoantibody testing and will receive a supply of doxycycline after they have been randomized into Group 2. They will begin taking doxycycline on Day 2, self-administering the antibiotic intermittently on Days 2-9, Days 22-24 and Days 32-38. Following randomization, they will have four scheduled clinic visits. The first two will be on Day 8 and Day 23, when they receive their first and second vaccinations with AV7909. Their third clinic visit will be on Day 37 when they will have a final blood draw for TNA and their fourth and final planned clinic visit will occur on Day 51 and includes a blood draw for TSH and autoantibodies.

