6.1.6. Administration of Doxycycline

Doxycycline (100 mg po q 12 hr) will be administered only to participants in Group 2. A total of 35 ± 2 doses will be administered in three courses as shown in [Figure 2](#).

Group 2A participants will nominally receive 20 of their 35 doxycycline doses in the clinic whereas Group 2B will nominally receive two of their 35 doxycycline doses in the clinic. The remaining doses will be taken at home. Doses should be taken at the same times \pm 30 min each day. Doses administered in the clinic will be recorded by the staff with the date and time of administration in each participant's source documents and eCRF. Doses self-administered at home will be recorded by the participant with the time of administration in their e-diary. Refer to [Section 8.3.5.1](#) for additional details on the e-diary. If a participant misses a dose, they should be instructed to take the dose as soon as remembered, but no later than 4 hours of its scheduled time. The participant should then wait until the next scheduled dose. The participant should not take two doses at the same time.

Exact details regarding the format in which the doses will be provided to the participants will be provided in the Pharmacy Manual.

Certain foods and over-the-counter products can interfere with the absorption of doxycycline so prior to administration of doses in the clinic, site staff should ask each participant if they have eaten certain dairy products (such as milk or yogurt) or taken magnesium/aluminum antacids, other highly buffered drugs, or other products containing calcium, iron or zinc since their last dose and if so record this information along with the timing of intake (eg, 6 hours since their last dose). This information along with other precautions that need to be followed when taking doxycycline will be provided to participants when they are given their supplies of doxycycline for self-administration (see [Section 5.3.1](#)).

AV7909 Anthrax Vaccine

IND 014451

Protocol EBS.AVA.210, Version 3.0 (28 October 2019)

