8.1.3.5. Group 1B: Days 31 to 36 (At home)

On Days 31 to 37, the participant is to self-administer ciprofloxacin 500 mg po every 12 hours at home [at about the same times (\pm 30 min) each day]. The participant will continue with the e-diary as described in [Section 8.3.5.1](#). The site must contact the participant to remind them to start their third course of ciprofloxacin within 24 hours of Day 31.

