8.1.5.4. Group 2B: Day 23 (± 1 day) – Vaccination #2

1. Staff will review the participant's doxycycline supply and review e-diary entries, conducting a compliance check of the remaining doses compared to the e-diary record. Staff will also discuss any changes in the use of concomitant medication as well as any vaccination reactions if still ongoing, and reminding the participant of the precautions in [Section 5.3](#).
2. Review and record AEs.
3. Perform symptom-directed PE, if required.
4. Record concomitant medications.
5. Assess vital signs (seated/semi-recumbent blood pressure, heart rate, respiratory rate, and temperature).

AV7909 Anthrax Vaccine

IND 014451

Protocol EBS.AVA.210, Version 3.0 (28 October 2019)

6. Review eligibility for continuing vaccination.
7. For WOCBP, collect and perform UPT (prior to AV7909 vaccination). Positive UPTs will be confirmed with a serum pregnancy test. All confirmed pregnancies in participants who receive at least one dose of any IP and where conception occurs prior to 12 months after last receipt of any IP will be followed to outcome.
8. Administer doxycycline 100 mg po in AM; the evening dose will be self-administered at home.
9. Administer AV7909 vaccination #2; this should occur after doxycycline dosing. Participants should be monitored for at least 30 minutes following vaccine administration for any adverse effects especially anaphylaxis.
10. Following the 30 (\pm 5) minutes of observation, repeat vital signs (seated/semi-recumbent blood pressure, heart rate, respiratory rate, and temperature) measurement.
11. After diary review, participants will be reminded to continue to use the reactogenicity e-diary and injection site reaction measurement tool, to capture any use of concomitant medications and to record the dates and times they self-administer their doxycycline doses on the antibiotic e-diary. See [Section 8.3.5.1](#).
12. Prior to discharge on Day 23, participants doxycycline supply will be returned, and participants will be reminded to return to clinic in two weeks (\pm 1 day) on Day 37 \pm 1d for the final blood draws for TNA. Again, participants are to continue dosing with doxycycline through the morning of Day 37.

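### Group 2B's Day 23 discharge instruction omits the doxycycline break that the schedule requires; followed literally it gives 47 doses against a stated 35 ± 2

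*Protocol*

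**What the plan says.** **Schedule sections.** Protocol Section 4.1.4 has Group 2B "self-administering the antibiotic intermittently on Days 2-9, Days 22-24 and Days 32-38". The Synopsis gives the same days for Group 2, and Table 8 lists Days 32-38 for the third course. The note to Figure 1 in Section 4.1 says that doxycycline stops after the doses around the second vaccination and resumes on Day 32. Section 6.1.6 adds: "A total of 35 ± 2 doses will be administered in three courses". Section 8.1.5.3 limits the second course to the day before, the day of and the day after vaccination.

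**Visit sections for Group 2B.**
- Section 8.1.5.4, item 12 (discharge on Day 23): "participants are to continue dosing with doxycycline through the morning of Day 37". No break is mentioned.
- Section 8.1.5.5: "On Days 32 to 37, the participant is to self-administer doxycycline 100 mg po every 12 hours at home". It then says: "The site must contact the participant to remind them to start their third course of doxycycline within 24 hours of Day 31".
- Section 8.1.5.6 ties the end of dosing to the blood draw if the Day 37 visit shifts.

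**Parallel Group 1B step.** Section 8.1.3.4, item 12, is built the same way but does state a break: the second course ends on the evening of Day 24, and nothing more is taken before Day 31.

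**The concern.** Item 12 is what site staff tell a participant who is about to leave the clinic and has no further scheduled visit until Day 37. It should match the schedule, and it does not. Someone who followed it as worded would take doxycycline on Days 25-31, which every schedule section leaves drug-free. Sections 4.2 and 4.3.3 give limiting antibiotic exposure in healthy volunteers as the reason for intermittent dosing.

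There is also a smaller analytic stake. Groups 2A and 2B are pooled as Group 2 in the Day 37 non-inferiority comparison with Group 3. Doses on Days 25-31 fall between the second vaccination and the toxin-neutralizing antibody (TNA) draw, so any Group 2B participant who took them would differ in exposure from Group 2A within the same arm.

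**Working it through.** **1. Reproduce the stated 35.** Two doses a day on the days in Section 4.1.4, morning dose only on Day 38:
- Days 2-9: 8 × 2 = 16
- Days 22-24: 3 × 2 = 6
- Days 32-37: 6 × 2 = 12
- Day 38, morning: 1
- Total: 16 + 6 + 12 + 1 = 35

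Two of these (the mornings of Days 8 and 23) are given in clinic, leaving 33 at home. That matches the Synopsis: "Group 2B self-administering 33/35 doses". The morning-only dose on Day 38 is stated for Group 2A (Section 8.1.4.13). For Group 2B it is inferred, because it makes both 35 and 33 come out.

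**2. Follow item 12 literally.** Dosing runs without a break from Day 22 to the morning of Day 37:
- Days 2-9: 16
- Days 22-36: 15 × 2 = 30
- Day 37, morning: 1
- Total: 16 + 30 + 1 = 47

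Against the schedule this adds 7 × 2 = 14 doses (Days 25-31) and drops 2 (Day 37 evening, Day 38 morning), a net 12 more. The ratio is 47/35 = 1.34, and 47 is 10 above the upper limit of 37. If the second vaccination moves to Day 22 or Day 24, the second course starts on Day 21 or Day 23. The literal totals become 16 + 32 + 1 = 49 or 16 + 28 + 1 = 45.

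**3. Keep the break and vary only the start and end of the third course.** The first two courses contribute 22 doses.

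| Last dose | Start Day 32 | Start Day 31 |
|---|---|---|
| Day 37 morning (8.1.5.4) | 22 + 11 = 33 | 22 + 13 = 35 |
| Day 37 evening (8.1.5.5) | 22 + 12 = 34 | 22 + 14 = 36 |
| Day 38 morning (implied by 35) | 22 + 13 = 35 | 22 + 15 = 37 |

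All six totals lie within 33 to 37. Table 8 adds a wrinkle: it lists Day 38 as an at-home day, and its footnote defines those as days with both doses taken at home. That gives 36 from a Day 32 start, still in range. Only both doses on Day 38 together with a Day 31 start leaves the range, at 38, and no section states that combination.

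**4. Timing against the TNA draw.** On the nominal schedule the draw follows the Day 37 morning dose. The two doses in dispute at the end of the course (Day 37 evening, Day 38 morning) come after it.

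**The case against.** The strongest reply is that nobody would dose continuously in practice. The schedule sections all show the break. Section 8.1.5.3 bounds the second course. Section 6.4 describes supply by course, the e-diary prompts doses at appropriate times (Section 8.3.5.1), and a call to start a third course presupposes that dosing had stopped. The schedule leaves 1 + 2 + 13 = 16 doses after the Day 23 clinic dose, whereas item 12 read literally needs 1 + 26 + 1 = 28. Unless 12 extra tablets are in hand, 47 cannot be reached.

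Most of that stands, and it makes 47 a worst case. It does not remove the contradiction. The quantity dispensed is set in the Pharmacy Manual, which is not available here. If exactly 16 doses were in hand and item 12 were followed, they would run out on the morning of Day 31, before the TNA draw. That too would depart from the schedule.

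The reply also has force on the reminder. Section 8.1.5.3 asks sites to call within 24 hours of the expected start of the second course, and a Day 31 call for a Day 32 start fits that pattern. The sentence may describe when the call is made, not when dosing begins.

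Four stronger readings may tempt a reader. The documents support none of them.
- **That the reminder produces 47 doses.** It does not. Only item 12 does. A Day 31 start moves the total by 2.
- **That the compliance denominator is undefined.** SAP Section 5.4.1 takes the required tablet count from Figure 2, not from the visit text. The figure is not reproduced in the text reviewed, so no fault in it can be claimed.
- **That the 50% rule for the Immunogenicity Population is compromised.** Half of 33, 34 or 35 is 17 to 18 doses, and a participant who took too many would still pass.
- **That Group 1B has the same problem.** Its discharge step states the break, and its count reproduces: 12 + 6 + 13 = 31. What remains is mainly a section heading.

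**Conclusion.** The contradiction is real and lies in Section 8.1.5.4, item 12. As worded, it gives 47 doses against 35, outside the stated 35 ± 2, by filling Days 25-31. It is a drafting inconsistency in an instruction that sites carry out, and the documents do not present it as an alternative regimen. The text governs 30 of about 70 Group 2 participants; that is the number it applies to, not a forecast of how many would follow it.

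The differing end days and the Day 31 reminder are secondary. Each leaves the total within 35 ± 2, and on the nominal schedule the disputed end-of-course doses come too late to affect the Day 37 sample. The primary endpoint is untouched, because Group 2B contributes no pharmacokinetic data.

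The counts assume two doses a day, a morning-only final dose on Day 38, and the second vaccination on Day 23 unless stated otherwise. The point still deserves correction before sites work from the text: the worst case is needless antibiotic exposure in healthy volunteers, measured against the protocol's own schedule.

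**What to change.** Reconcile Section 8.1.5.4, item 12, with Sections 4.1, 4.1.4 and 6.1.6 and Table 8, so that the discharge step says explicitly whether there is a break and on which days it begins and ends. In the same edit, bring the end of the third course and the reminder day in Sections 8.1.5.5 and 8.1.5.6 into line with those sections, and state in Table 8 how many doses fall on the last day. The sponsor decides which schedule is intended.

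As a minor tidy-up, align the heading of Section 8.1.3.5, which stops at Day 36, with its text: "On Days 31 to 37, the participant is to self-administer ciprofloxacin". That text should also agree with the Figure 1 note that Group 1 takes no evening dose on Day 37.

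The cost is a protocol clarification and a memo to sites. Sample size, endpoints and analysis methods do not change.

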8.1.5.6. Group 2B: Day 37 (\pm 1) – Blood Draw for TNA

The Day 37 Visit may shift by \pm 1 day. If such a shift occurs, the participant must remain on doxycycline 100 mg po every 12 hours until the morning before the blood draw. In the event of such a shift, the participant's required number of doses of doxycycline will vary. The Pharmacy Manual will contain a table detailing the dosing options for the final course of doxycycline given a one-day shift from Day 37.

1. Participants will report to the clinic having taken their morning dose of doxycycline at home.
2. Review participant's doxycycline supply; count the number of remaining doses and compare to the e-diary record to document compliance; record total remaining in source document.
3. Review other e-diary entries with participant. Discuss any changes in the use of concomitant medication as well as any vaccination reactions if still ongoing. Remind

AV7909 Anthrax Vaccine

IND 014451

Protocol EBS.AVA.210, Version 3.0 (28 October 2019)

participants that they should still use sunscreens and avoid excessive sun exposure and strenuous sports until the Day 51 Final Study Visit.

4. Record concomitant medications.
5. Collect blood sample for TNA assessment.

8.1.5.7. Group 2B: Day 51 (± 1d) – Final Study Visit

1. Perform complete PE.
2. Review e-diary entries with participant and collect hand-held device if study provided.
3. Review and record AEs.
4. Record concomitant medications.
5. Assess vital signs (seated/semi-recumbent blood pressure, heart rate, respiratory rate and temperature).
6. For WOCBP, collect and perform UPT. Positive UPTs will be confirmed with a serum pregnancy test. All confirmed pregnancies in participants who receive at least one dose of AV7909 or doxycycline and where conception occurs prior to 12 months after last receipt of either IP will be followed to outcome.
7. Collect blood sample for hematology.
8. Collect blood sample for serum chemistry.
9. Collect blood sample for TSH and autoantibodies.
10. Collect urine sample for urinalysis.

8.1.6. Group 3: AV7909 Alone

Shown in [Table 9](#) is a schedule of events for Group 3 participants from screening until the end of the study. Following the table are detailed descriptions of the activities that the sites are expected to conduct for each of the column headings identified in the table once each participant has received his or her group assignment. Note that for Group 3 this detail only includes Days 8 and 23 as the detailed activities during Screening and Group Assignment (Randomization) were covered previously in [Section 8.1.1](#) and the activities for the Day 37 and Day 51 visits, the Safety Follow-up Phone calls and the EWVs are handled individually in [Section 8.1.6.3](#), [Section 8.1.6.4](#), [Section 8.1.7](#), and [Section 8.1.8](#), respectively.

Table 9: Schedule of Events for Group 3: AV7909 Alone

	Screening	Group Assign	Vac	TNA	Final Visit	Safety Calls	EWV USV‡
Study Day(s)	-28 to -2	1	8 23*	37	51	114, 205, 296, 388	NA
Visit Window ±	NA	NA	±1d*	±1d	± 1d	± 14d	
Sign, date ICF & assign ID	X						
Review eligibility ^a	X	X	X				

AV7909 Anthrax Vaccine

IND 014451

Protocol EBS.AVA.210, Version 3.0 (28 October 2019)

	Screening	Group Assign	Vac	TNA	Final Visit	Safety Calls	EWV USV‡
Study Day(s)	-28 to -2	1	8 23*	37	51	114, 205, 296, 388	NA
Visit Window ±	NA	NA	±1d*	±1d	± 1d	± 14d	
Medical history & demographics	X	X					
Physical examination ^b	X				X		X
ECG ^c	X						
Vital signs ^d	X	X	X		X		X
Pregnancy test ^e	X	X	X		X		X
FSH test ^e	X						
Collect sample for hematology ^f	X				X		X
Collect sample for serum chemistry ^g	X				X		X
Collect sample for urinalysis ^h	X				X		X
Urine drug screen ⁱ	X						
HIVAb/HBsAg/HCVAb	X						
Concomitant medications ^j	X	X	X	X	X	X	X
Randomize eligible participants		X					
Symptom-directed PE ^k		X	X				
Blood draws for TNA ^l		X		X			
AV7909 vaccination ^m			X				
Participant e-diary + tools ⁿ			X	X	X		X
AEs ^o , SAEs & AESIs ^p	X	X	X		X	X	X
Collect TSH & autoantibody sample ^q		X			X		X

For the abbreviations used above please refer to [Table 1](#).

*± 1 d window only applies to the second vaccination (Day 23). ‡For EWV occurring within the visit window of Day 37, a blood sample for TNA will be drawn,

^a Eligibility will be reviewed before each vaccination, ie, on Day 8 and Day 23.

^b Physical examinations (PE) will be conducted as described in [Protocol Section 8.3.3](#).

^c An ECG will be conducted at screening as described in [Protocol Section 8.3.3](#).

^d Vital signs will be administered as described in [Protocol Section 8.3.4](#).

^e Pregnancy tests (serum and/or urine) will be administered to all WOCBP as described in [Protocol Section 8.3.2](#). Serum pregnancy test will be performed at Screening visit for WOCBP, while urine pregnancy tests for WOCBP will be required before each vaccination. At Screening visit only, FSH test will be performed for postmenopausal women.

^f Hematology will be conducted as described in [Protocol Section 8.3.2](#).

^g Serum chemistry will be conducted as described [Protocol Section 8.3.2](#).

^h Urinalyses will be conducted as described in [Protocol Section 8.3.2](#).

ⁱ Urine drug screens will be conducted as described in [Protocol Section 8.3.2](#).

^j Concomitant medications will be identified and recorded as described in [Protocol Section 6.5](#).

^k Symptom-directed PEs will be conducted as described in [Protocol Section 8.3.3](#).

^l Blood samples for TNA assessment on Day 1 will be collected in the morning following randomization. Those on Day 37 will be collected in the morning. A TNA sample will also be collected if EWV occurs within the visit window of Day 37 as described in [Protocol Section 8.1.8](#).

^m Vaccinations with AV7909 will be administered as described in [Protocol Section 6.1.3](#).

ⁿ All participants will be provided with an e-diary for post vaccination follow up along with a thermometer and an injection site reaction measurement tool and will be trained on the use of these tools and the e-diary as described in [Protocol Section 8.3.5.1](#).

^o AEs will be collected at all clinic visits through Day 51/EWV as described in detail in [Protocol Section 9](#).

^p SAEs and potential AESIs will be collected during the Safety Follow-up Telephone Calls (see [Protocol Section 8.1.7](#)).

^q Serum samples for TSH & autoantibody testing will be collected from all participants and tested as described in [Protocol Section 8.1.6.3](#) (ie, at Day 1, Day 51, and at EWV if the subject received at least one vaccination). Additional samples for TSH &

AV7909 Anthrax Vaccine

IND 014451

Protocol EBS.AVA.210, Version 3.0 (28 October 2019)

autoantibody testing may be collected based on the safety follow-up phone contact if warranted from participant report(s) of a potential AESI); blood draws for additional TSH and/or autoantibody testing should be performed as part of an unscheduled visit.

